8.2.4. Psoriasis Symptoms Diary (PSD)

The PSD assesses the severity of symptoms or how bothersome are the symptoms of psoriasis. The PSD will be analyzed as follows:

- Change and percent change from baseline to Weeks 2, 4, and 8 in the PSD individual item and total scores will be analyzed using descriptive statistics and an ANCOVA (total score only) with terms for country, baseline S-IGA category, and baseline B-IGA category, and baseline PSD score as a covariate. Statistical comparisons between the treatment groups will be obtained using contrasts. The LS means, standard errors, 95% CIs, and *P* values will be presented. Only change from baseline in PSD total score at Weeks 4 and 8 using the ITT population will be included in the testing strategy.

8.3. Exploratory Efficacy Analysis

Exploratory efficacy analysis will be performed for subjects belonging to ITT and mITT populations.

The exploratory endpoints include:

- Achievement of success in PASI-90, PASI-75, and PASI-50 at Weeks 2, 4, 8, and 9
- Time to success in PASI-50
- Change and percent change from baseline in PASI/mPASI at Weeks 2, 4, 8, and 9
- Change and percent change from baseline in WI-NRS at Weeks 2, 4, and 8
- For subjects with baseline WI-NRS score ≥ 4 , achievement of ≥ 4 -point improvement from baseline in WI-NRS at Weeks 2, 4, and 8 (summarized on the PRU4-ITT and PRU4-mITT populations)

- Change and percent change from baseline in DLQI/CDLQI total scores at Weeks 2, 4, and 8
- Change and percent change from baseline in % BSA affected by disease at Weeks 2, 4, 8, and 9

Time to success in PASI-50 and change and percent change from baseline for all relevant exploratory endpoints will be summarized descriptively; additionally, all endpoints will be analyzed using an ANCOVA with terms for country, baseline S-IGA category, and baseline B-IGA category, and baseline assessment score as a covariate. Statistical comparisons between the treatment groups will be obtained using contrasts. The LS means, standard errors, 95% CIs, and *P* values will be presented. Achievement of success in PASI-50, PASI-75, and PASI-90; achievement of success in mPASI-50, mPASI-75, and mPASI-90; and improvement in WI-NRS will be presented using proportions. Odds ratios and 95% CIs of the odds ratios will be provided. Additionally, the 95% Wilson CIs for proportion of successes in each treatment group will be presented.

For efficacy analysis purposes, the data that is collected by the ePRO will be used for % BSA affected by disease summarization.

9. Safety and Tolerability Analysis

Safety will be evaluated from reported AEs, physical examinations, local tolerability assessments, changes in clinical laboratory values, changes in vital signs/weight, C-SSRS, PHQ-8, and modified PHQ-A results. No inferential statistical tests will be performed.

All safety analyses will be performed on the Safety population.

9.1. Adverse Events

All AEs, TEAEs, and SAEs will be coded using the MedDRA dictionary version 23.0.

A TEAE is defined as an AE that started post application of IP at the Baseline visit through study completion. An overall summary of TEAEs will be provided; this will present number and percent of subjects who reported at least 1 of the following: TEAE (including all TEAEs, TEAEs by maximum severity, and TEAEs by greatest relationship), SAE, discontinued the study due to a TEAE, or a TEAE resulting in death.

The number and percent of subjects reporting TEAEs, grouped by MedDRA system organ class (SOC) and preferred term, will be tabulated by severity or greatest relationship to study IP and treatment group. In the case of multiple occurrences of the same TEAE within the same subject, each subject will only be counted once for each preferred term. Additionally, the number and percent of subjects reporting related TEAEs will be summarized by MedDRA preferred term and treatment group.

In the summaries showing severity and relationship to study medication the event with the maximum severity (mild < moderate < severe) or strongest relationship (not related < related) will be reported. If a particular event is missing the severity and/or relationship, then the strongest possible severity or relationship will be assumed for analysis (severity = severe, relationship = likely).

In the AE data listings, all AEs will be displayed. Any AEs that are treatment emergent will be flagged.

9.1.1. Adverse Events Leading to Withdrawal

A summary of incidence rates (frequencies and percentages) of TEAEs leading to withdrawal of study drug by treatment group, SOC, and preferred term will be prepared for the Safety population. Additionally, this table will be repeated for TEAEs leading to withdrawal from the study. No inferential statistical tests will be performed.

A data listing of AEs leading to withdrawal of study drug will also be provided, displaying details of the event(s) captured on the eCRF.

9.1.2. Deaths and Serious Adverse Events

Any deaths that occur during the study will be listed.

Serious adverse events (SAEs) will be listed and tabulated by SOC and preferred term and presented by treatment group, severity, and relationship to study treatment.

9.2. Local Tolerability Assessments

The investigator's assessment of the application site reaction will be summarized by study visit using both categorical methods (number and percentage of subjects with each score) as well as continuous methods (e.g., mean, median). Categorical summaries will be provided for dermal response as well as other effects. No inferential statistical tests will be performed.

The subject's assessment of the application site reaction will be summarized similarly.

9.3. Clinical Laboratory Evaluations

Laboratory test results will be summarized descriptively by treatment and study visit as both observed values and change from baseline values for continuous hematology, chemistry, and urinalysis results. Categorical urinalysis results will be summarized using frequencies by study visit and treatment.

The number of subjects with clinical laboratory values below, within, or above the normal range by study visit and in relation to baseline will be tabulated for each clinical laboratory analyte by treatment group (shift table).

Abnormal results will be flagged in the listings. In addition, pregnancy test results and hormonal laboratory results will be listed.

9.4. Vital Signs

Descriptive summaries of observed values and changes from baseline will be calculated for systolic blood pressure, diastolic blood pressure, heart rate, height, weight, BMI, and oral body temperature by treatment group and visit.

The number of subjects who gain or lose $\geq 5\%$ of their baseline body weight during the course of the study, as well as subjects who gain or lose $\geq 10\%$ of their baseline body weight over the course of the study, will be summarized by treatment group. This summary will be repeated by intentionality of weight loss (intentional or unintentional, as captured on the eCRF).

Shift tables for subjects who shift from their baseline BMI category as defined in Section 6.1.7 (underweight, normal, overweight, obese) to a different BMI category throughout the course of the study will be provided by treatment group and visit. This summary will be repeated by intentionality of weight loss (intentional or unintentional, as captured on the eCRF).

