#### **6.4.6 Clinical Laboratory Results and Vital Signs/Weight Measurements**

All clinical laboratory results and vital signs measurements and their change from baseline (pre-dose), will be summarized along with time point of collection.

A shift table describing out-of-normal range shifts from Baseline will be provided for clinical laboratory results.

Shift tables will identify subjects who gain or lose >5% body weight over the course of the study, as well as subjects who gain or lose >10% body weight over the course of the study.

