14.3.6 Other Safety Data Summary Tables		
Table 14.3.6.1	Safety	Shift from Baseline in Patient Health Questionnaire (PHQ-8)/Modified PHQ-Adolescents by Study Visit
Table 14.3.6.2.1	Safety	Summary of Investigator Local Tolerability Assessment by Study Visit
Table 14.3.6.2.2	Safety	Summary of Investigator Local Tolerability Assessment (Dermal Response) by Study Visit Categorical Results
Table 14.3.6.2.3	Safety	Summary of Investigator Local Tolerability Assessment (Other Effects) by Study Visit Categorical Results
Table 14.3.6.3.1	Safety	Summary of Subject Local Tolerability Assessment by Study Visit
Table 14.3.6.3.2	Safety	Summary of Subject Local Tolerability Assessment by Study Visit Categorical Results
Table 14.3.6.4.1	Safety	Summary of Vital Signs by Study Visit
Table 14.3.6.4.2	Safety	Shift from Baseline in Weight by Study Visit
Table 14.3.6.4.3	Safety	Shift from Baseline in Weight by Study Visit and Weight Loss Intentional/Non-Intentional Categories
Table 14.3.6.4.4	Safety	Shift from Baseline in BMI Categories by Study Visit
Table 14.3.6.4.5	Safety	Shift from Baseline in BMI Categories by Study Visit and Weight Loss Intentional/Non-Intentional Categories
Table 14.3.6.5	Safety	Summary of Columbia-Suicide Severity Rating Scale (C-SSRS) Suicidal Ideation and Suicidal Behavior by Study Visit
Table 14.3.6.6	Safety	Summary of Physical Examination by Study Visit
Table 14.3.6.7	Safety	Summary of Concomitant Medications by ATC Class Level 4 and Preferred Term

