2 = Moderate (definite warm, tingling sensation)	XX (XX.X%)	XX (XX.X%)	XX (XX.X%)
3 = Severe (hot, tingling/stinging sensation)	XX (XX.X%)	XX (XX.X%)	XX (XX.X%)
Week 4			
0 = None (no sensation)	XX (XX.X%)	XX (XX.X%)	XX (XX.X%)
1 = Mild (slight warm, tingling sensation)	XX (XX.X%)	XX (XX.X%)	XX (XX.X%)
2 = Moderate (definite warm, tingling sensation)	XX (XX.X%)	XX (XX.X%)	XX (XX.X%)
3 = Severe (hot, tingling/stinging sensation)	XX (XX.X%)	XX (XX.X%)	XX (XX.X%)

Repeat for Week 8

Abbreviation: IP = investigational product.

Note: Percentages are n/Number of subjects in the Safety Population within treatment received and overall*100. Baseline for subject local tolerability assessment is the last non-missing measurement taken on the day of first application of study drug. These assessments should be done 10 - 15 minutes after the application of IP in the study site. Subjects not meeting this condition on baseline visit are completely removed from the table summary.
Reference Listing: 16.2.9.2

Table 14.3.6.4.1
Summary of Vital Signs by Study Visit
Safety Population

(Same shell as Table 14.3.5.1.1; visits include Baseline, Week 2, Week 4, Week 8, Week 9; parameters include Temperature (°C), Heart Rate (bpm), Systolic Blood Pressure (mmHg), Diastolic Blood Pressure (mmHg), Height (cm), Weight (kg), and BMI (kg/m^2) [1], where [1] goes to "[1] Body Mass Index (BMI) = weight (kg) / [height (m)]²."; Reference Listings: 16.2.9.3.1, 16.2.9.4.2)

Table 14.3.6.4.2
 Shift from Baseline in Weight by Study Visit
 Safety Population

Study Visit Category	Roflumilast Foam 0.3% (N=XX)	Vehicle (N=XX)	Overall (N=XX)
Week 2			
Weight Loss \geq 10%	XX (XX.X%)	XX (XX.X%)	XX (XX.X%)
Weight Gain \geq 10%	XX (XX.X%)	XX (XX.X%)	XX (XX.X%)
Weight Loss \geq 5%	XX (XX.X%)	XX (XX.X%)	XX (XX.X%)
Weight Gain \geq 5%	XX (XX.X%)	XX (XX.X%)	XX (XX.X%)
Week 4			
Weight Loss \geq 10%	XX (XX.X%)	XX (XX.X%)	XX (XX.X%)
Weight Gain \geq 10%	XX (XX.X%)	XX (XX.X%)	XX (XX.X%)
Weight Loss \geq 5%	XX (XX.X%)	XX (XX.X%)	XX (XX.X%)
Weight Gain \geq 5%	XX (XX.X%)	XX (XX.X%)	XX (XX.X%)
Week 8			
Weight Loss \geq 10%	XX (XX.X%)	XX (XX.X%)	XX (XX.X%)
Weight Gain \geq 10%	XX (XX.X%)	XX (XX.X%)	XX (XX.X%)
Weight Loss \geq 5%	XX (XX.X%)	XX (XX.X%)	XX (XX.X%)
Weight Gain \geq 5%	XX (XX.X%)	XX (XX.X%)	XX (XX.X%)
Continue for Week 9			

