Note: Percentages are n/Number of subjects in the Safety population within treatment received and overall*100. Baseline is the last non-missing measurement taken before the first application of study drug.
 Reference Listing: 16.2.9.3.2

Table 14.3.6.4.3
Shift from Baseline in Weight by Study Visit and Weight Loss Intentional/Non-Intentional Categories
Safety Population

(Same shell as Table 14.3.6.4.2, except will be presented by the following categories as headers in the by-line: “Weight Loss: Intentional” and “Weight Loss: Not Intentional or Missing”).

Table 14.3.6.4.4
Shift from Baseline in BMI Categories by Study Visit
Safety Population

Study Visit	Post-Baseline Category [1]	Baseline Category Roflumilast Foam 0.3% (N=XX)				Total
		Missing	Underweight	Normal	Overweight	
Week 2	Missing	XX (XX.X%)	XX (XX.X%)	XX (XX.X%)	XX (XX.X%)	XX (XX.X%)
	Underweight	XX (XX.X%)	XX (XX.X%)	XX (XX.X%)	XX (XX.X%)	XX (XX.X%)
	Normal	XX (XX.X%)	XX (XX.X%)	XX (XX.X%)	XX (XX.X%)	XX (XX.X%)
	Overweight	XX (XX.X%)	XX (XX.X%)	XX (XX.X%)	XX (XX.X%)	XX (XX.X%)
	Obese	XX (XX.X%)	XX (XX.X%)	XX (XX.X%)	XX (XX.X%)	XX (XX.X%)
Total	XX (XX.X%)	XX (XX.X%)	XX (XX.X%)	XX (XX.X%)	XX (XX.X%)	XX (XX.X%)
Week 4	Missing	XX (XX.X%)	XX (XX.X%)	XX (XX.X%)	XX (XX.X%)	XX (XX.X%)
	Underweight	XX (XX.X%)	XX (XX.X%)	XX (XX.X%)	XX (XX.X%)	XX (XX.X%)
	Normal	XX (XX.X%)	XX (XX.X%)	XX (XX.X%)	XX (XX.X%)	XX (XX.X%)
	Overweight	XX (XX.X%)	XX (XX.X%)	XX (XX.X%)	XX (XX.X%)	XX (XX.X%)
	Obese	XX (XX.X%)	XX (XX.X%)	XX (XX.X%)	XX (XX.X%)	XX (XX.X%)
Total	XX (XX.X%)	XX (XX.X%)	XX (XX.X%)	XX (XX.X%)	XX (XX.X%)	XX (XX.X%)

Repeat for Vehicle and Overall. Repeat all for Week 8.

Abbreviation: BMI = body mass index.

Note: Percentages are n/Number of subjects in the Safety population within treatment received and overall*100. Baseline is the last non-missing measurement taken before the first application of study drug. BMI is derived as (weight in kg)/[(height in cm/100)²].

[1] If BMI is below 18.5 then it is categorized as underweight; if BMI ranges between 18.5 – 24.9 then it is categorized as Normal; if BMI ranges between 25.0 – 29.9 then it is categorized as overweight; if BMI is ≥ 30.0 then it is categorized as obese.

Reference Listings: 16.2.9.4.1, 16.2.9.4.2

Table 14.3.6.4.5
Shift from Baseline in Weight by Study Visit and Weight Loss Intentional/Non-Intentional Categories
Safety Population

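### The SAP promises the number of subjects whose weight changed by 5% or 10% over the study, but its table shells count by visit only; the C-SSRS table footnote has a related mismatch

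*SAP*

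**What the plan says.** **Weight, text.** SAP 9.4 commits to the number of subjects who gain or lose at least 5% "of their baseline body weight during the course of the study, as well as subjects who gain or lose" at least 10% "of their baseline body weight over the course of the study, will be summarized by treatment group". It adds: "This summary will be repeated by intentionality of weight loss". Protocol 6.4.6 says: "Shift tables will identify subjects who gain or lose >5% body weight over the course of the study", and the same for more than 10%. The protocol uses > where the SAP uses ≥.

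**Weight, shells.** Table 14.3.6.4.2 in SAP 14.2 is titled "Shift from Baseline in Weight by Study Visit". It has blocks for Weeks 2, 4 and 8 and ends with the instruction "Continue for Week 9". Table 14.3.6.4.3, listed in SAP 13.1.3 as "Shift from Baseline in Weight by Study Visit and Weight Loss Intentional/Non-Intentional Categories", is specified as "Same shell as Table 14.3.6.4.2, except will be presented by the following categories as headers in the by-line". Percentages in the weight shell use the whole Safety population of each group.

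**C-SSRS.** SAP 6.1.7 defines ideation, behavior and their composite by a positive answer at any point while on treatment. The footnote to Table 14.3.6.5 likewise says that it counts subjects who had the event one or more times on treatment. SAP 9.6 refers to a positive response at any point but has it summarized by visit and group. The shell has blocks for Screening, Baseline Day 0, Week 4 and Week 8.

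**The concern.** The natural safety question is how many subjects ever crossed the threshold. The weight text promises that number; the shells replace it with four cross-sections. A subject who crosses 5% at Week 2 and then leaves appears in the Week 2 row only. A subject who crosses and stays there appears in every row.

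The harms are not incidental. Protocol 3.3.2 names weight loss and psychiatric events as known effects of oral roflumilast, and safety is part of the primary objective. Protocol 4.4.3 lists both unintended weight loss above 5% and a C-SSRS indicating ideation as possible grounds for stopping the product. A report programmed to the shells would omit the promised weight count and carry a C-SSRS footnote that misdescribes part of its own table.

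**Working it through.** The plan states no figure on this point, so there is none to reproduce. The check compares text with shells, then works out what visit rows can and cannot determine.

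**1. Is the count produced anywhere?**

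| Item | Text | Shell |
|---|---|---|
| Change of 5% or 10% in weight | Over the study, by treatment group (SAP 9.4; protocol 6.4.6) | Weeks 2, 4, 8, 9 |
| Same, by intentionality | Repeat of the above (SAP 9.4) | Same four visits |
| C-SSRS ideation, behavior, composite | Any point on treatment (SAP 6.1.7; table footnote); by visit (SAP 9.6) | Screening, Baseline, Weeks 4, 8 |

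The Overall column pools treatment groups, not visits. The planned safety tables in SAP 13.1.3 include no other weight-threshold or C-SSRS summary.

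**2. Can visit rows be turned into subjects?** Let v₁, …, vₖ be the visit-row counts and A the number of subjects with the event at any time.

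- Always: A ≥ max(vᵢ).
- Only if every qualifying value sits in a visit row: A ≤ Σvᵢ.

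The counts below are assumed, because the documents give none. The planned active arm is about 200.

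- Weight rows 1, 1, 2, 2: max = 2, and 2/200 = 1.0%; sum = 1+1+2+2 = 6, and 6/200 = 3.0%.
- Weight rows 2, 4, 6, 6: max = 6, and 6/200 = 3.0%; sum = 2+4+6+6 = 18, and 18/200 = 9.0%.
- C-SSRS rows 1, 1 (Weeks 4 and 8): max = 1, and 1/200 = 0.5%; sum = 2, and 2/200 = 1.0%.

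Persistent weight loss would put A near the lower figure. The upper figure needs every row to hold different subjects.

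**3. Does the condition for the upper limit hold?** Not necessarily for weight. SAP 6.1.5 admits unscheduled, repeat and early-termination values to a visit row only when the scheduled value is absent. Suppose a subject's scheduled Week 2 weight is below the threshold, and the subject leaves with an early-termination weight above it, still on or before Day 22, the end of the Week 2 window. That second value enters no row. In the first example, one such subject who is in no other row gives A of up to 6+1 = 7, and 7/200 = 3.5%, above the row sum.

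For C-SSRS this matters less. The early-termination visit follows Week 9 content (protocol 5.5), which includes weight but no C-SSRS, and no text requires an unscheduled C-SSRS.

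**4. Which C-SSRS blocks does the footnote fit?** Screening is a lifetime summary (SAP 9.6). Baseline precedes treatment, since a positive score there bars enrollment (protocol 5.1.8). The footnote is wrong for both. Weeks 4 and 8 use the form that looks back to the previous visit, so each block does count on-treatment events, but for one interval only.

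**The case against.** **Weight.** By-visit counts might satisfy the text. In the same SAP section, the BMI sentence also speaks of change throughout the study and delivers it by visit. Protocol 6.4.6 asks for shift tables, in a section that summarizes results with their collection time point. This is a permissible reading, but the weaker one. The BMI sentence says explicitly that it is by group and visit, as does the opening sentence of SAP 9.4; the weight-threshold sentence says by treatment group only.

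**C-SSRS.** SAP 9.6 is the governing analysis text, and it says by visit; the list title and shell agree. A reader might infer that the plan commits to a separate any-time C-SSRS table. It does not: the any-time wording stands in a derivation and a footnote, and the phrase in SAP 9.6 is tied to visits. A reader might also infer that the footnote describes nothing in its table. That goes too far, because Weeks 4 and 8 are on-treatment intervals. What stands is a footnote that misdescribes two blocks and three derived variables with no output matching their definition.

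**Consequence.** Percent weight change and intentionality are in Listing 16.2.9.3.2, and C-SSRS is in Listing 16.2.9.8. Both kinds of event go to the medical monitor under protocol 5.1.4 and 5.1.8. Safety has no inferential tests. All of this stands and keeps the point minor.

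**Conclusion.** The mismatch holds. The study-level weight count in SAP 9.4 and protocol 6.4.6 is not produced by any planned table and cannot be recovered from the visit rows. The C-SSRS part is secondary: the derived variables and the footnote do not match a by-visit shell.

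The size of any discrepancy is unknown. The any-time count is at least the largest visit row. A reader might take the sum of the rows as a firm ceiling, but SAP 6.1.5 does not support that, since some qualifying values may sit in no row.

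A reader might also infer that early suicidal ideation goes unseen or that safety data are lost. The documents do not support either: the Week 4 form covers the time since the previous visit, and the subject-level data are listed. The cost of leaving the plan alone is that someone must count affected subjects by hand from listings. No test, estimate or conduct rule changes. Severity is minor. Confidence is high that the rows are missing, and lower that an any-time C-SSRS count was ever meant as a reporting commitment.

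**What to change.** 1. Add an any-time post-baseline block to Tables 14.3.6.4.2, 14.3.6.4.3 and 14.3.6.5, counting each subject once per row.
2. In Table 14.3.6.5, apply the on-treatment footnote to that block only, and label the Screening block as lifetime.
3. Add to SAP 6.1.5: the scheduled-value-first rule governs by-visit rows; any-time rows use all post-baseline values, including unscheduled and early-termination values.
4. Intentionality is recorded by visit, so Table 14.3.6.4.3 needs an assignment rule. Place a subject in the not-intentional-or-missing category if any qualifying loss is so marked.

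Items 3 and 4 correct no stated error; they make the new block unambiguous.

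The cost is four rows for weight (loss and gain at two thresholds), 4 × 2 = 8 by intentionality, and up to 14 for C-SSRS: ideation and its 5 items (6), behavior and its 4 items (5), suicide, the composite, and non-suicidal self-injury (3). All use data already collected. The downsides are slightly more programming and counts that may be higher than those in the visit rows.

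The alternative is to narrow the wording of SAP 9.4, SAP 6.1.7 and the footnote to by-visit counts. That would remove the inconsistency within the SAP, but it would give up the more useful number and leave protocol 6.4.6 unmet on its natural reading.

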9.5. PHQ-8 and Modified PHQ-A

Data for PHQ-8 and modified PHQ-A will be classified using each subject's total score at a time point into a category based on the following scoring system:

- None – Minimal depression (0 to 4)
- Mild depression (5 to 9)
- Moderate depression (10 to 14)
- Moderately severe depression (15 to 19)
- Severe depression (20 to 24)

Shift tables showing the category of severity at each visit by treatment group will be presented.

9.6. C-SSRS

The C-SSRS is a questionnaire that prospectively assesses Suicidal Ideation and Suicidal Behavior. At the Screening study visit, “Baseline/Screening” version of the C-SSRS will be used. This version assesses Suicidal Ideation and Suicidal Behavior during the subject's lifetime and during the past 6 months. For the Screening visit, “lifetime” experience of the subject with Suicidal Ideation and Suicidal Behavior will be summarized. From Baseline visit, the “Since Last Visit” version will be used.

Suicidality data collected on the C-SSRS will be listed for all subjects. Tables will include results from the Suicidal Ideation and Suicidal Behavior sections of the C-SSRS. Frequencies and percentages of subjects with a response of “Yes” at any point on the Suicidal Ideation and Suicidal Behavior items will be summarized by study visit and treatment group.

